**Protocol Synopsis:**

Arthroscopy of the temporomandibular joint (TMJ) is a well-established surgical procedure for treating various TMJ disorders. The technique involves inserting an arthroscope into the joint cavity, followed by the insertion of a working cannula through which the surgeon's instruments pass. Successfully inserting the working cannula requires advanced surgical skills and extensive clinical experience, as mastering this technique has a steep learning curve. Incorrect placement of the working cannula can cause iatrogenic damage to the TMJ and adjacent structures, including the facial nerve and ear. It is generally accepted that if the working cannula cannot be inserted successfully after 2-3 attempts, the procedure should be halted.

In our department, we developed a guide device we called Locator-Positioner (LOPO) to aid surgeons in precisely inserting the working cannula into the joint cavity. This device makes the insertion process predictable and straightforward. The aim is to ensure the smooth and accurate placement of the working cannula, allowing it to be immediately visible through the arthroscope, and eliminating unnecessary movements that could harm the joint tissue and nearby structures.

The prototype of the LOPO was tested on anatomical models and proved to be highly accurate. In all insertion attempts, the working cannula – guided by the device – was placed precisely and became immediately visible by the arthroscope.

This pilot study aims to recruit up to 10 patients to test the LOPO device in a clinical setting.

**Background:**

Temporomandibular joint (TMJ) problems can present a wide range of symptoms, including difficulty opening the mouth, inability to close the mouth, noises during jaw movement, temporary mechanical locking episodes, and pain in the TMJ and masticatory muscles. These issues can adversely affect daily activities like eating, speaking, and yawning, thereby reducing patients' quality of life.

Arthroscopy of the TMJ was first introduced in 1976 and has since become a recognized therapeutic method for treating TMJ issues. The procedure begins with the insertion of the arthroscope into the posterior part of the joint cavity. Subsequently, a "working cannula" is placed in the anterior part of the joint cavity. The surgeon's instruments are then inserted through this working cannula during the procedure.

Similar to arthroscopy performed on other joints like the knee and shoulder, a tube is connected to the arthroscope during the procedure to flow a flushing fluid (isotonic saline or similar fluids) into the joint cavity, maintaining constant pressure within the joint space. The saline infusion is automatically triggered when the pressure drops. In TMJ surgeries, a fluid pressure of around 40 PSI is used. This lavage system ensures continuous hydro-distension (inflation with water) of the joint cavity, enabling clear vision and facilitating the surgeon's work. If the fluid pressure inside the joint drops, the joint capsule collapses onto the intra-articular structures, obstructing the view through the lens of the arthroscope.

As previously mentioned, the initial stage of the operation involves inserting the arthroscope into the rear part of the TMJ. This step is relatively straightforward because the proximity of the joint to the ear provides a visible landmark for the surgeon. The anatomical landmarks constituting the ear, eye, and cheekbone aid this approach. Conversely, inserting the working cannula into the front part of the joint is more challenging due to significant anatomical variation among individuals and lack of easy landmarks to rely on. Therefore, facial skin landmarks cannot reliably guide this insertion and the triangulation technique was described as an alternative. This technique involves creating a spatial relationship between three points: the arthroscope, the target area within the joint, and the working cannula's entry point. The term "triangulation" refers to the coordination between the visual axis of the arthroscope and the working cannula's path. The surgeon uses the arthroscope to guide the working cannula to the correct position within the joint. Successful insertion of the working cannula hinges on three conditions: 1) ensuring it avoids damaging nearby vital structures both during and after insertion, 2) positioning it directly within the arthroscope's field of view in the front part of the joint for immediate visibility, and 3) achieving successful insertion on the first attempt, with a maximum allowance for additional 1 or 2 attempts if necessary.

Successful arthroscopy relies on accurately placing the working cannula ideally on the first attempt, and at most on the second or third attempts. Multiple attempts to insert the cannula can lead to puncturing of the joint capsule, causing leakage of the irrigation fluid (saline) and swelling of the face. This edema not only discomforts the patient but also compromises sufficient inflation (hydro-distension) of the joint cavity, thereby complicating the surgical procedure. Scientific literature generally advises halting the procedure after few unsuccessful attempts to insert the working cannula into the correct position.

Furthermore, repeated attempts increase surgical risks, including potential damage to facial nerve branches, blood vessels in the face, and the auditory canal, as well as heightened post-operative pain.

#### **Reasoning behind conducting the experiment:**

We developed a guide device referred to as Locator-Positioner (LOPO) designed to assist surgeons in accurately and precisely inserting the working cannula into the TMJ. Following the initial insertion of the arthroscope into the joint, which is a relatively straightforward procedure, the LOPO is attached to the outer part of the arthroscope (remaining external to the skin of the face). The LOPO then provides guidance to the surgeon on where and how on the skin to insert the working cannula to precisely align with the end of the arthroscope found within the joint.

Importantly, the LOPO does not enter the patient's body at any point during the operation and should not touch or rest on the skin of the patient's face. It securely attaches to the outer part of the arthroscope, indicating the insertion point and guiding the cannula at the correct angle. Following successful testing on anatomical models, where it demonstrated exceptional accuracy, we aim to evaluate its clinical effectiveness in up to 10 patients to draw conclusive findings.

**Description of the device:**

The guide device consists of two arms of equal length, each being a double parallelogram. A connector holds both arms and permits movement by changing the angle between them (Fig 1). One arm is intended to hold the arthroscope while the other arm holds the working cannula. Owing to the double parallelogram design, after attaching the instruments (arthroscope and working cannula) their ends have to meet, and this is true in the whole range of motion of the guide device, so that while changing the angle between the two arms of the LOPO, the meeting point between the tip of the arthroscope and the tip of the working cannula keep their intimate relation (Fig 1 and 2).

During surgery, after the arthroscope is introduced into the joint cavity, the guide device is mounted on the base of the arthroscope via one arm. The other arm receives the working cannula, and owing to the double parallelogram design, it directs it to the ideal puncture site and insertion vector and depth into the joint cavity, where it has to meet the tip of the arthroscope (Fig 3). This results in immediate visualization of the working cannula by the arthroscope and maintains optimal spatial positions between the two portals. The connector between the two arms of the device enables changing the angle between them while maintaining the relative position of the tip of the cannula to the tip of the arthroscope.

The connector can also be locked thus fixating the angle between the two arms.

Throughout the range of motion, the working cannula will always reaches the tip of the arthroscope. The LOPO does not enter the body because only the ends of the arthroscope and the working cannula are inside the body while the device is externally positioned and held by the surgeon.

The LOPO is designed to address the challenges of determining the insertion point on the skin for the working cannula, the correct angle for insertion into the joint cavity, and the proper penetration depth. In addition, it maintains the optimal spatial orientation between the arthroscope and cannula throughout surgery. Its main goal is to ensure that the working cannula is inserted accurately and becoming immediately visible via the arthroscope on the first attempt, and them maintaining the correct spatial relationship between the arthroscope and the working cannula throughout surgery.

Figure 1: the yellow lines represent the path of insertion of the arthroscope and working cannula. The red asterisk represents the meeting point of both. Through all range of motion

of the LOPO device (changing the angle between its' two arms), the ends of both instruments maintain their relations to one another.

[figure not shown]
[figure not shown]
[figure not shown]

Figure 2: the LOPO with the arthroscope and working cannula mounted on it.

Figure 3: illustration demonstrating the relations between the TMJ, arthroscope (blue), working cannula (red), and LOPO guide device (grey).

#### **Technical details:**

- Manufacturer: Pollak Steinberg Ltd.
- Model: TMJ-DEVICE-100
- Materials: Stainless steel 303, resistant to autoclave sterilization, multi-use
- The device can be attached and detached from the arthroscope and working cannula at any stage of the operation.

#### **Summary of existing preclinical knowledge regarding the device:**

The device was tested on anatomical models between August 2017 and February 2018, and it was found to meet the objectives exceptionally well. Multiple doctors in the department,

including interns with no prior arthroscopy experience, conducted several attempts on the models. In all cases, the working cannula was guided by the LOPO device and inserted with great precision to the end of the arthroscope, where it was immediately visible by it. The experiments were conducted in the operating room at Sheba Medical Center using the same set of standard arthroscopic tools.

In this pilot experiment, we will use the same standard set of arthroscopic tools that is regularly used at Sheba Medical Center. It is important to note that the LOPO has been designed according to the dimensions of the arthroscopic tool set available at Sheba.

### **Goals and Endpoints**

This pilot study aims to recruit up to 10 patients to test the functionality of the LOPO in clinical conditions. The outcome of the study are:

1. The number of attempts required by the surgeon to correctly place the instruments in relation to each other within the joint cavity. No more than three attempts will be made in a single operation.
2. The time elapsed from the insertion of the working cannula until it is clearly visible by the arthroscope (measured in seconds).
3. The number of cases in which the surgeon fails to correctly insert the working cannula, meaning that after three attempts, the cannula is still not properly placed in the joint and not visible by the arthroscope.
4. The improvement of mouth opening after arthroscopy.

Our hypothesis is that the LOPO will shorten the duration of surgery by helping the surgeon insert the working cannula more quickly and easily. It should allow accurate insertion of the working cannula on the first attempt, reducing scuffing of tissues, fluid leakage, swelling, and surgical risks. Using the device does not increase the known risks of surgery.

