**Method of Analyzing and Processing Results:**

- The data from the ten patients using the device will be compared with data from patients undergoing TMJ arthroscopy without using the LOPO device. The following parameters will be evaluated:
  - o Time elapsed from insertion of the working cannula until it is clearly visible through the arthroscope.
  - o Number of attempts made by the surgeon to correctly position the instruments within the joint cavity (limited to three attempts per surgery, following standard practice).
  - o Number of cases where the surgeon failed to correctly insert the working cannula, despite three attempts, as observed through the arthroscope.

- Measurements of maximal mouth opening of the patients undergoing the procedure, before as compared to after arthroscopy.

Contact:

[name]

Telepohone: [name]

Email: [[contact]](mailto:[contact]), [[contact]](mailto:[contact])

[name]

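### The hypothesis is shorter surgery, but operating time is not an outcome, and the only clock appears to start after LOPO mounting and puncture-site finding

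*Protocol*

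**What the plan says.** Protocol, Goals and Endpoints, states the hypothesis: "Our hypothesis is that the LOPO will shorten the duration of surgery by helping the surgeon insert the working cannula more quickly and easily". The same section lists four outcomes: number of attempts, one time, number of failures after three attempts, and improvement in mouth opening. The time is "The time elapsed from the insertion of the working cannula until it is clearly visible by the arthroscope (measured in seconds").

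Method of Analyzing and Processing Results lists the same four items, with the same start and stop for the time. It says that the LOPO data "will be compared with data from patients undergoing TMJ arthroscopy without using the LOPO device".

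Two sections give the order of steps. In Reasoning behind conducting the experiment, once the arthroscope is in the joint, "the LOPO is attached to the outer part of the arthroscope", and "The LOPO then provides guidance to the surgeon on where and how on the skin to insert the working cannula". Description of the device agrees: with the arthroscope in the joint, "the guide device is mounted on the base of the arthroscope via one arm", and the other arm takes the cannula and directs it to the puncture site. That section also says "The LOPO is designed to address the challenges of determining the insertion point on the skin for the working cannula", followed by angle and depth, and gives the aim: "Its main goal is to ensure that the working cannula is inserted accurately and becoming immediately visible via the arthroscope on the first attempt".

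**The concern.** The duration part of the hypothesis has no outcome that can test it. The one interval that is timed seems to begin after two steps that differ between the groups. Mounting is extra work that only LOPO patients have. Finding the skin entry point is a task that the device is meant to make easier, and comparison patients have it done freehand. Leaving out the first could flatter the device; leaving out the second could hide part of its benefit.

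The Protocol plans journal publication. A shorter insertion-to-view time could then be read as confirming shorter surgery, although that was not measured. Mounting and site-selection times that are not stamped during the operation cannot be recovered at analysis, so a later analysis plan could not repair this.

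**Working it through.** **Step 1: match hypothesis to outcomes.**

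| Item in Goals and Endpoints and in the analysis section | A time? | Operating time? |
|---|---|---|
| Number of attempts | No | No |
| Cannula insertion to clear view | Yes, in seconds | No |
| Failures after three attempts | No | No |
| Mouth opening | No | No |

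The hypothesis also expects accurate insertion on the first attempt, which the attempts outcome covers. Only the duration part is unmatched.

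**Step 2: place the clock in the sequence of steps.** From the two device sections, the LOPO order is: arthroscope in the joint, device mounted, skin site indicated, cannula inserted, cannula seen. The clock covers only the last part, from insertion to view. Of the three challenges that the device addresses, guidance of angle and depth falls at least partly inside the clock. Finding the insertion point falls before it. Without the LOPO there is no mounting, and freehand site selection precedes insertion.

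**Step 3: relate the reported saving to the saving in placement.** Define, in seconds:

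- F, L: insertion-to-view time without and with LOPO
- P: freehand site selection before first insertion
- S: LOPO mounting and site finding before first insertion
- D = F − L, the saving that the plan would report
- X = S − P

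From a common start at arthroscope in position, the saving is

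(P + F) − (S + L) = (F − L) − (S − P) = D − X.

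It vanishes at X = D, exceeds D when X is negative, and is a loss when X is greater than D.

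**Step 4: illustrate.** The Protocol gives no times, so every D and X here is assumed. Entries are D − X in seconds; negative means longer with LOPO.

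| | X = −30 | X = 0 | X = 60 | X = 120 |
|---|---|---|---|---|
| D = 30 | 60 | 30 | −30 | −90 |
| D = 60 | 90 | 60 | 0 | −60 |
| D = 120 | 150 | 120 | 60 | 0 |

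**Step 5: repeat attempts.** Up to three attempts are allowed. If the clock runs from first insertion to final view, re-siting between attempts is already inside F and L, and the identity holds with S and P as defined. If the clock restarts at each attempt, failed attempts and re-siting are also untimed and must be added to S and P. The Protocol does not say which applies.

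**Step 6: from placement to surgery.** If A is any time saved after the cannula is seen, the saving over these steps and the rest of the operation is D − X + A. The Protocol says that the device keeps the two instruments aligned throughout surgery, so A need not be zero. The plan measures D but neither X nor A.

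**The case against.** The best defence is that this is a pilot of function. The hypothesis names its mechanism, quicker and easier insertion, and the first three outcomes address that. The sample size is justified by effective positioning, not by shorter surgery, and insertion-to-view time suits the stated main goal of immediate visibility. This stands: the interval is worth keeping, and the mismatch is confined to the duration claim.

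Second, *insertion* is undefined, and elsewhere the Protocol uses the word loosely for the whole step, site choice included. Technical details also says that the device can be attached or detached at any stage. The first part stands as a caution: that mounting and site finding go untimed is the plain reading, not a certainty. But two observers could then start the clock at different points, which itself needs fixing. Being attachable at any stage does not change the order that the device sections describe.

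Third, the illustrative values have no basis in the documents and include more positive than negative values of X. This stands too. The table shows how the conclusion depends on X and is not evidence of bias in either direction.

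Fourth, total operating time may be kept in routine records, and up to 10 patients with a comparison not described as randomised could not isolate the device's effect on it. The Protocol is silent on such records. The second part is a reason to report operating time descriptively and to narrow the claim, not to leave the hypothesis as worded.

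**Conclusion.** The concern holds. Shorter surgery is hypothesised, and no outcome or analysis parameter measures it; that follows directly from the text. That mounting and puncture-site finding fall outside the only clock rests on reading *insertion* as the cannula entering the skin, the natural reading given the order of steps.

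The size and direction of the omission are unknown. The saving from arthroscope in position to view is D − X, and the Protocol gives neither quantity. As written, the plan can support a statement about how soon the cannula is seen once inserted. It cannot support one about placement as a whole or the duration of surgery. The attempts and failure outcomes are unaffected. This should be fixed before patients are operated on, because the missing stamps must be taken at the time.

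**What to change.** - Define the start and stop of each interval in Goals and Endpoints, and repeat the definitions in the analysis section.
- In both groups, record the time from arthroscope in position, before any LOPO mounting or site selection, to cannula clearly visible, with all attempts included.
- Keep insertion-to-view time as a component, and state whether its clock runs on across attempts or restarts.
- Record total operating time and report it descriptively only.
- If the comparison data lack these stamps, limit the hypothesis and the conclusion to insertion-to-view time.

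The cost is a change of wording and one or two extra time stamps per operation. The reported saving may turn out smaller, or the conclusion narrower if the comparison data cannot supply the stamps.

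### An operation abandoned after one or two misses with no cannula placed is not a failure as the protocol defines it, because failure requires three attempts and three is only a maximum

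*Protocol*

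**What the plan says.** Protocol, Goals and Endpoints, outcome 1 is "The number of attempts required by the surgeon to correctly place the instruments", with the limit "No more than three attempts will be made in a single operation". Outcome 3 is the number of cases in which the surgeon fails to insert the working cannula correctly, and the protocol defines this as "meaning that after three attempts, the cannula is still not properly placed in the joint and not visible by the arthroscope".

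Protocol, Method of Analyzing and Processing Results, lists the same quantities for comparison with patients operated on without the device. The attempts outcome becomes "Number of attempts made by the surgeon to correctly position the instruments within the joint cavity", which is "limited to three attempts per surgery, following standard practice". The failure outcome becomes "Number of cases where the surgeon failed to correctly insert the working cannula, despite three attempts, as observed through the arthroscope".

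Two background statements bear on when a surgeon might stop. The Protocol Synopsis reports a general view that "if the working cannula cannot be inserted successfully after 2-3 attempts, the procedure should be halted". The Background adds that "repeated attempts increase surgical risks, including potential damage to facial nerve branches".

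**The concern.** The failure definition has two parts: the cannula is not placed, and three attempts have been made. The second part would be harmless if every unsuccessful operation ran to three attempts, but the protocol sets three only as an upper limit. A surgeon who stops after one or two misses breaks no rule in the document. One who stops after two is within the range that the synopsis calls generally accepted. That patient ends without a working cannula and is still not counted under outcome 3.

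Outcome 3 is the outcome closest to the purpose of the device. The group has at most 10 patients, so a single case separates a report of no failures from a report of one. The attempts outcome does not make up for this, since on attempts made the abandoned case looks like a good result.

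**Working it through.** The protocol states no failure rate, threshold or sample-size formula for this outcome, so there is no figure of its own to reproduce. The check is mainly textual, with one small illustration.

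**Step 1. Is the three-attempt condition relaxed anywhere?** No. Goals and Endpoints sets it with the word *after*, and the analysis section repeats it with *despite*. No other section gives a wider definition.

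**Step 2. Is a third attempt required anywhere?** No. Both sections that mention three in connection with conduct use it as a ceiling. The synopsis and the Background describe general practice and surgical risk. They are not trial rules, but they make a stop before the third attempt foreseeable.

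**Step 3. Classify each possible ending under the current wording.**

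| How the attempts end | Failure (outcome 3) | Attempts made (analysis section) | Attempts required to place (outcome 1) |
|---|---|---|---|
| Placed on attempt 1 | No | 1 | 1 |
| Placed on attempt 2 | No | 2 | 2 |
| Placed on attempt 3 | No | 3 | 3 |
| Three misses, not placed | Yes | 3 | No value |
| Two misses, stopped, not placed | **No** | **2** | No value |
| One miss, stopped, not placed | **No** | **1** | No value |

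The last two rows are the problem. Neither is a failure as written. On attempts made, each scores below a third-attempt success (2 < 3 and 1 < 3) and ties with a success on the second or first attempt. A three-miss case also ties with a third-attempt success on attempts made, but outcome 3 does count it.

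**Step 4. Size, as an illustration.** Inputs: n = 10, the stated maximum for the LOPO group; one abandoned case and no other failure, which is an assumption. The intervals are exact (Clopper-Pearson) 95% limits for x failures in n: the lower limit is the 2.5% point of Beta(x, n − x + 1), or 0 when x = 0, and the upper limit is the 97.5% point of Beta(x + 1, n − x).

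- As written, x = 0: 0/10 = 0%, with upper limit 1 − 0.025^(1/10) = 0.3085, so 0% to 30.8%.
- If the case is counted, x = 1: 1/10 = 10%, with lower limit 1 − 0.975^(1/10) = 0.0025 and upper limit 0.445, so 0.3% to 44.5%.

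If enrolment ends sooner, the denominator shrinks and each case weighs more. With n = 9, the counts are 0/9 (0% to 33.6%) as written and 1/9 = 11.1% (0.28% to 48.25%) if counted.

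**Step 5. Effect on the comparison.** Let *a* of n₁ LOPO patients and *b* of n₂ comparison patients be abandoned early and not counted. The reported difference in failure proportions (LOPO minus comparison) then differs from the true one by −a/n₁ + b/n₂. The protocol gives neither *a*, *b* nor n₂, so the sign cannot be determined.

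**The case against.** The strongest reply is that the rule is clear in context: the surgeon tries until success or until the limit, and a case that reaches the limit unplaced is a failure. On that reading the 2–3 in the synopsis is only background, and no trial-specific section describes ending an operation after two misses. Part of this stands. The background text is not a trial rule, and a reader who takes it as an instruction to stop at two goes too far. But the natural reading still depends on every unsuccessful operation reaching three attempts, which nothing requires. If the intent is to count any unplaced case, the proposed wording simply says so.

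A second reply is that Conditions for Halting the Medical Experiment would bring such a case to light, because performance below that seen on the anatomical models stops use of the device and further enrolment. This also stands in part. A reader might infer that several failures among 10 patients could go uncounted. The halting rule makes that hard to sustain, since one abandoned case may end enrolment, and this is also why 10 completed patients is only an assumption here. But the halting rule governs use of the device and recruitment. It does not classify the operation under outcome 3.

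A third reply is that scoring of unplaced cases is commonly left to the SAP, which is not shown. That is fair for the exact score. It does not answer the failure definition, which the protocol does not leave open: it fixes the definition twice, with the limiting condition each time.

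**Conclusion.** The point holds and is minor. As written, an operation whose cannula attempts end after one or two misses with nothing placed is not a failure, and on attempts made it looks better than a third-attempt success. Within either group, the wording can only lower the failure count or leave it unchanged.

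The effect depends entirely on whether any operation is stopped early. The protocol gives no basis for a frequency, and if none is stopped early, nothing changes. In the illustration, one case shifts the LOPO count by one: 1/10 against 0/10 with 10 patients, or a larger proportion if enrolment ends sooner.

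A reader might infer that the definition favours the device in the comparison. The documents do not support that. The same definition applies to patients operated on without the LOPO, and early stops there would lower their count too, so the direction of any net effect is unknown. The point also does not extend to operations in which the device is detached, as Technical details permits, and the cannula is then placed freehand. Those end with a cannula in place and raise a different question.

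**What to change.** In both Goals and Endpoints (outcome 3) and Method of Analyzing and Processing Results, replace the three-attempt condition with wording such as: *failure is any operation in which attempts to insert the working cannula end, within the maximum of three, without a cannula that is correctly placed and visible through the arthroscope.*

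For the attempts outcome, add that an operation ending without placement must not count as better than a successful one. The exact score or ranking can be left to the SAP. Apply both rules alike to LOPO and comparison patients.

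The cost is a change of wording in two sections. LOPO patients need no extra data, since the number of attempts and whether the cannula was placed are already to be recorded. For comparison patients, the sponsor should check that their records identify operations ended before a third attempt. If they do not, the revised definition cannot be applied equally and the report should say so.
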